The study titled *Population Based Prospective Annual Assessment of Safety of Romiplostim Treatment in Adult Patients with Chronic ITP Based on National Health Registry Systems in Denmark, Sweden, and Norway* is also known as the “Nordic Country Patient Registry for Romiplostim (NCPRR).” The NCPRR is a patient registry established on the basis of the National Health Registry Systems (NHRS) of 3 Nordic countries: Denmark, Sweden, and Norway. Patients who receive romiplostim therapy between January 2009 and December 2019 will be included in the patient registry through the existing NHRS databases.

The purpose of the NCPRR is to obtain long-term data on the safety of romiplostim therapy and to fulfill romiplostim post-approval pharmacovigilance (PV) requirements.

Primary Objective

- To estimate the incidence rate of increased bone marrow (BM) reticulin and/or BM fibrosis with associated clinical signs¹, confirmed by BM biopsy findings in adults with chronic ITP receiving romiplostim

Secondary Objectives

Potential clinical risks:

- To describe the phenomenon of worsened thrombocytopenia (platelet count significantly reduced to, or below, baseline platelet count levels) after romiplostim cessation among adult chronic ITP patients
- To study the incidence rate of thrombocytosis (platelet count > 450 x 10⁹/L) among romiplostim-treated adult chronic ITP patients with/without adverse events
- To describe the incidence rate of thrombotic/thromboembolic events, and the distribution of specific diagnoses of these thrombotic/thromboembolic events for a romiplostim-exposed cohort and an unexposed cohort
- To assess the incidence rate of hematological malignancies and pre-malignant states (focused on acute myelogenous leukemia [AML] and myelodysplastic syndromes [MDS]) for a romiplostim-exposed cohort and an unexposed cohort

¹ Clinical signs: any of the following: splenomegaly, hepatomegaly, leukocytosis, and cytopenia.

- To describe clinically significant bleeding and/or receipt of rescue medication (any new ITP medication prescribed to a chronic ITP patient during romiplostim therapy) in predefined romiplostim therapy periods ([Section 7.1](#))
- To describe the incidence rate of concurrent leukocytosis and anemia (measured by laboratory test results taken within 4 weeks of each other)
- To describe patient safety profiles, including the incidence rate of renal failure among adult chronic ITP patients with renal impairment medical condition at the time romiplostim therapy is initiated
- To measure the impact of the EU dosing rule in the cohort of romiplostim exposed patients

Potential BM abnormal findings:

- To describe the prevalence of reticulin and collagen fiber content in the first BM biopsy of adult chronic ITP patients prior to romiplostim exposure, by splenectomy status
- To assess the incidence of collagen fibrosis with associated clinical signs confirmed by findings in BM biopsies of adults with chronic ITP either receiving or not receiving romiplostim
- To study the incidence of chronic idiopathic myelofibrosis (CIMF, primary myelofibrosis) according to the World Health Organization (WHO) diagnostic criteria for adults with chronic ITP either receiving or not receiving romiplostim
- To assess overall and specific incidence of BM fibrosis, including reticulin and collagen fiber content formation, and CIMF among adult chronic ITP patients using BM data prior to and following romiplostim therapy, regardless of clinical signs and symptoms in adults with chronic ITP either receiving or not receiving romiplostim

Romiplostim Off-label Use:

- To describe the romiplostim utilization pattern in patients without adult chronic ITP

Hypotheses

The NCPRR is descriptive in nature for the purpose of hypothesis generation. There is no specific hypothesis for each specific outcome of interest.

Study Design

The NCPRR is established on the basis of the NHRS of 3 Nordic countries: Denmark, Sweden, and Norway.

The study period will be between 01 January 2009 (starting date) and 31 December 2019 (ending date). Interim study reports will be developed for yearly submission to the Agency. Each annual report will describe events occurring from 01 January through 31 December of the reporting period with cumulative results. All data sources will use the same cutoff date in calendar time, December 31st of the latest year for all data obtained from the NHRS databases. The patient experience (patient time) for all patients who receive at least 1 dose of romiplostim therapy will be

included in the romiplostim exposure cohort after they receive romiplostim. The patient experience with ITP before romiplostim exposure will be included in the romiplostim unexposed cohort along with that for all adult chronic ITP patients who never receive romiplostim therapy during the study period.

Adult chronic ITP cohorts (romiplostim “Exposed Cohort” and “Unexposed Cohort”) will include adult patients identified as having chronic ITP (incident and prevalent cases identified through both hospital discharge registry and outpatient clinic registry, as described by [Frederiksen and Schmidt, 1999](#)) on or after the starting date, and up to 1 year prior to the ending date. All patients will be followed-up for **at least 1 year and up to 11 years** in either the romiplostim Exposed Cohort or Unexposed Cohort. Incident and recurrent outcomes of interest will be assessed on an annual basis.

All clinical outcomes (eg, thrombotic/thromboembolic events, hematological malignancies, and other potential outcomes of interest) will be identified by International Classification of Diseases – 10th Revision (ICD-10) codes from the NHRS databases (eg, hospital discharge registry, outpatient clinic registry, pathology registry, death registry, cancer registry, birth registry, and prescription registry) or by review of electronic medical records and/or paper medical charts. As needed, suspected and identified cases will be medically confirmed by review of electronic medical records and/or paper medical charts, laboratory test results, BM biopsy reports, pathology data, pharmacy data, and other relevant health records. Laboratory data will be used to determine thrombocytosis and worsened thrombocytopenia after cessation of romiplostim.

Because ITP is a diagnosis of exclusion and secondary causes of thrombocytopenia may be difficult to diagnose, some patients will require review of medical records and laboratory data including bone marrow exams, if any, prior to their first diagnosis of ITP (ICD-10: D69.3-D69.4). These will include the relevant time periods prior to their first diagnosis of ITP for all patients who have a history of any condition from [Appendix 2](#) prior to the first diagnosis of ITP.

Cases with either increased BM reticulin or BM fibrosis (with/without associated clinical signs) and cases of hematological malignancies or disorders (eg, AML and MDS) will be ascertained using electronic medical record review. Confirmation of the diagnosis of reticulin/collagen BM, reticulin/collagen fibrosis or hematological malignancies and disorders will be carried out by evaluation of the results of BM biopsies.

The 3 selected Nordic countries gather all health-related data on their citizens through a complex system of interlinked databases. The Danish government, for example, has compiled nearly 200 registry databases (some initiated in the 1930s) on everything from medical records, hospitalization, prescriptions, laboratory and pathology results, a cancer registry, and death certificates to socioeconomic data regarding jobs and salaries. What makes the databases a prime research tool is the fact that they are all linked by the 10-digit personal identification

number, called CPR, that follows each Danish citizen from birth to death. The NHRS and related databases in Norway and Sweden are similar to Danish system.

Selected data fields for each adult chronic ITP patient (prevalent cases as of 01 January 2009, and incident cases thereafter), and patients who receive romiplostim therapy during the study period, will be extracted and analyzed to evaluate the endpoints listed in [Section 6.2](#). These selected data fields include those for the patient population using other thrombopoietic agents, since these agents could have a confounding impact on the occurrence of study outcomes such as BM fibrosis. In addition, the study will last up to 11 years, and will include both prevalent cases between 1996 and 2008 and incident cases from 2009 to 2018. The diagnoses, treatment procedures, medications, and practice patterns may be significantly changed; therefore, the study will use an inception cohort approach to define the study cohort based upon year of initial ITP diagnosis. Depending upon the sample size, the inception cohorts may be established for the following periods: 1996 to 2000, 2001 to 2005, 2006 to 2010, 2011 to 2015, and 2016 to 2018. Patients and incident rate study outcomes will be compared among these inception cohorts.

To describe the romiplostim off-label utilization pattern, the study will also include patients without an adult chronic ITP diagnosis, but who are exposed to romiplostim. An example would be the inclusion of patients diagnosed with pediatric ITP, MDS, HIV/AIDS diagnoses, and who have received romiplostim therapy. Patients exposed to romiplostim with off-label use will be directly identified by drug codes for romiplostim as the codes are adopted in each participating country.

The selected NHRS databases have been previously used to determine the safety profile of pharmaceuticals, and have been considered among the best PV and epidemiology tools by regulatory authorities, epidemiologists, and safety specialists in both clinical medicine and research communities ([Frank, 2000](#)).

Prospective annual analyses will be conducted for the study, in which all proposed research outcomes will be assessed. The annual assessments will be descriptive in nature due to the small sample size and uncertainty of the diagnosis of some outcomes for each assessment. Results from these annual assessments and safety data from other sources (eg, clinical trials, US Patient Safety Registry [PSR], and Canada PSR) will be communicated in the appropriate context to the regulatory agency through submission of the romiplostim Periodic Safety Update Report (PSUR). In the event that a significant risk is observed in an annual assessment, an urgent ad hoc report will be submitted to the regulatory agency in the time frame defined by Amgen Standard Operating Procedures (SOPs).

The registry also can serve as an infrastructure to assess any other newly detected safety signals during post-marketing; however, new research outcomes must be reviewed and approved by the NCPRR Scientific Committee before they may be added to the study. Such modification of the study protocol will be communicated to the regulatory agency.

Primary Endpoints

- Incidence of increased BM reticulin and/or BM fibrosis with associated clinical signs², confirmed by findings in BM biopsies among adult chronic ITP patients
- Incidence of reticulin and collagen BM fibrosis (reticulin fibrosis and collagen fibrosis: SNOMED codes: M49000, M49001, M49020, M99611) with associated clinical signs, confirmed by findings in a BM biopsy among adults chronic ITP patients

Secondary Endpoints

Clinical Endpoints:

- Average platelet counts prior to, during, immediately after treatment cessation, and post-romiplostim therapy (study periods are defined in [Section 7.1](#))
- Incidence of thrombocytosis (laboratory confirmation of a platelet count > 450 x 10⁹/L) with/without associated symptoms or adverse events among adult chronic ITP patients
- Incidence of thrombotic/thromboembolic events (ICD-10: 180, 126)
- Incidence rate of hematological malignancies focused on AML and/or MDS
- Incidence of clinically significant bleeding and/or receipt of rescue medication for each predefined romiplostim treatment period ([Section 7.1](#))
- Incidence of concurrent leukocytosis and anemia (measured by laboratory test results taken within 4 weeks of each other)
- Description of platelet counts and dose adjustment in µg/kg of romiplostim in patients with cITP according to dose adjustment rules specified in the European SPC

BM Endpoints:

- Prevalence of reticulin and collagen fiber content in the first BM biopsies of adult chronic ITP patients prior to romiplostim therapy by splenectomy status
- Incidence of collagen fibrosis with associated clinical signs confirmed by findings in BM biopsies among adult chronic ITP patients
- Incidence of PMF (primary myelofibrosis, ICD-10: c94.5) according to the WHO diagnostic criteria in adult chronic ITP patients who have BM data prior to and/or post romiplostim therapy
- Overall and specific incidence rate of BM fibrosis, including reticulin and collagen fiber content formation, and PMF among adult chronic ITP patients with BM data prior to and/or post romiplostim therapy
- Association between the aforementioned primary and secondary clinical outcomes and BM abnormal findings

² Clinical signs: any of the following: splenomegaly, hepatomegaly, leukocytosis, and cytopenia.

- Association of changes in peripheral blood with listed BM abnormal findings (3 to 6 months prior to, 3 months prior to 3 months post, and 3 to 6 months post-BM abnormal findings)

Romiplostim Off-label Use:

- Romiplostim utilization in patients without adult chronic ITP assessed by underlying disease for which romiplostim is used

Study Setting

The post-marketing romiplostim patient registry will be established on the basis of the NPRS of Denmark, Sweden, and Norway.

Estimated Sample Size

The exact sample size for the NCPRR is unknown, and is projected based upon the estimated national figure of adult chronic ITP patients, as well as the anticipated percentage of adult chronic ITP patients who may be treated with romiplostim. Based upon a conservative estimate, the study will have at least 623 adult chronic ITP patients who will receive romiplostim therapy during the study period, which will equate to more than 4,000 patient-years of follow-up. The NHRS of these 3 countries may also be capable of providing records for approximately 1,860 adult chronic ITP patients who are not exposed to romiplostim, which should provide more than 12,700 patient-years of follow-up data.

Summary of Subject Eligibility Criteria

The study population is chronic ITP patients, defined as those who have been diagnosed with ITP for more than 6 months, and who continually receive ITP treatments (eg, ITP medication), and/or have had a splenectomy procedure. Any adult (≥ 18 years) chronic ITP patient who has received at least 1 dose of romiplostim therapy, and who is registered in the NHRS of Denmark, Sweden, and Norway between 01 January 2009 and 31 December 2018, will be eligible subjects for this study. Patients will be continually followed up after discontinuation of romiplostim therapy.

Patients are excluded from the cohorts of chronic ITP patients if either of the following is present:

1. Any diagnosis of another condition associated with thrombocytopenia other than chronic ITP listed in [Appendix 2](#) at any time prior to or within 6 months after the qualifying diagnosis for chronic ITP. Examples of thrombocytopenia associated with other diseases and conditions include systemic lupus erythematosus (SLE), HIV infection, hepatitis C virus infection, malignancy, lymphoproliferative disorders, and myelodysplastic syndrome.
2. Lack of a platelet count below $150 \times 10^9/L$ without obvious cause in the 6 months before or after their first ITP diagnosis code

Comparison Group

Adult chronic ITP patients who are never exposed to romiplostim during the study period will be in the comparison group known as the romiplostim Unexposed Cohort. If patients in the comparison

group receive a romiplostim therapy in the subsequent annual assessment period, they will be re-classified into the romiplostim Exposed Cohort. Due to selection bias resulting from confounding by indication, comparative analyses will be inherently challenging to interpret. Therefore, any comparative analysis will be considered as exploratory for signal detection and for the purpose of hypothesis generation. In addition, according to initial dates of receiving romiplostim therapy among patients in Exposed Cohort, the follow-up time period will be separated into 2 periods: (1) follow-up time period prior to romiplostim exposure, and (2) follow-up time period following romiplostim exposure. Patient experiences in the follow-up time period prior to the initial date of receiving romiplostim therapy will be considered as another “within-patient” comparison with the patient experiences during the follow-up time period after the initial date of receiving romiplostim therapy.

Study Period and Method of Follow-up

This registry will be a part of Amgen’s global effort to assess the safety of romiplostim treatment. Together with the *US Patient Safety Registry (PSR)*, the *Canada Patient Safety Registry (CPSR)*, the *US Immunogenicity Registry*, and the *US Pregnancy Registry*, Amgen will effectively assess identified and potential risks related to romiplostim therapy. The NCPRR has also been specifically designed to fulfill post-marketing PV requirements from the European regulatory authority, and will continue for 11 years (from 01 January 2009 through 31 December 2019).

Data Collection, Including Safety Data Collection

Although there is no specific need to collect data directly for each individual patient, the study may conduct additional data collection to fill some specific data gaps as needed (eg, BM data confirmation through a standard review process). No direct safety data will be collected from patients through this study, but it is possible that the study may actively review selected medical charts to confirm cases that may identify some adverse events that are specifically linked to romiplostim.

Procedures

Please refer to the [study design section](#) above.

Statistical Considerations

The NCPRR is descriptive in nature for the purpose of hypotheses generation. There is no specific hypothesis for each specific outcome of interest.

Patient records will provide person-years of data for each study cohort (Exposed and Unexposed). The incidence rates will be assessed for both the exposure and non-exposure cohorts. The incidence rates will also be assessed for both the follow-up time periods prior to and after the initial date of receiving romiplostim in the Exposed Cohort.

When sample size permits, Kaplan-Meier survival curves will be constructed for patients with events of interest for the Exposed Cohort and Unexposed Cohort.

Due to the intrinsic limitations of this type of observational study, the effects of confounding by indication may bias the results when the incidence rates of study outcomes are compared between the Exposed Cohort and Unexposed Cohort. The effects associated with confounding by indication will be considered in all analyses in order to reduce the possible impact of these effects in the comparison.

In order to reduce the effects of confounding by indication, a propensity score will be developed for each adult chronic ITP patient. A stratified analysis (by propensity score strata, disease severity, and platelet count) and multiple regression analyses will be carried out. As needed, the age-, sex-, and propensity score-matched approach may be also applied to the adult chronic ITP study population. (Inherent limitations related to propensity score are addressed in [Section 8](#)).

Cox regression models using romiplostim exposure as a time-varying covariate may be used to compare the event rates among ITP patients and the reference cohort, with an estimation of the hazard ratio and associated 2-sided 95% confidence interval. Other treatment exposures, health status, and disease condition may also be considered for inclusion in the model as time-varying covariates. The analysis will adjust for potential confounders and propensity score. Multiple event models such as Andersen-Gill models may be used to evaluate recurrent events if applicable. However, this analysis is only intended to serve exploratory and hypothesis generation purposes.

Means and 95% confidence intervals of laboratory numerical outcomes (eg, platelet counts) will be obtained and compared between the associated cohorts, and among different predefined time periods related to romiplostim treatment ([Section 7.1](#)).

All cases with BM fibrosis will be described in detailed narratives with respect to underlying disease, comorbidities, treatment history, medications, any possible risk factors, and demographic characteristics. This descriptive data will be summarized in the clinical study report.

All romiplostim-exposed patients who develop hematologic malignancies will be described in detailed narratives with respect to underlying disease, comorbidities, treatment history, medications, any possible risk factors, and demographic characteristics. This descriptive data will be summarized in the clinical study report.

Special analyses will be conducted for chronic ITP patients with renal impairment medical conditions at the time romiplostim therapy is initiated. The analysis will include multivariate analysis justifying for renal comorbidities and/or medical history, as well as stratified analysis based on renal impairment status at romiplostim therapy initiated. Other outcomes listed in this study proposal will also be described within each predefined stratum.

Analysis for romiplostim off-label users is descriptive in nature for the purpose of hypothesis generation. The analyses will describe the off-label study population in different study time periods.

Since comparative analyses will be inherently challenging to interpret, any comparative analyses will be considered as exploratory for signal detection and for the purpose of hypothesis generation. The study will also compare the incidence rates from the romiplostim exposed cohort to that from other potential sources where sufficient data may be present:

- Amgen Study 20080092 (Nplate™ Patient Safety Registry – Canada version)
- Amgen Study 20080045 (Nplate™ Patient Safety Registry – US version)
- Amgen Study 20070796 (Determination of Frequency Rates of Bone Marrow Fibrosis and Thrombotic/Thromboembolic Events in Patients with Chronic Immune (Idiopathic) Thrombocytopenic Purpura in Denmark)
- Administrative databases such as SEER, Ingenix, and GPRD, if appropriate data are available at time of analysis
- Published data on the frequency of predefined risks, such as [Mufti et al \(2007\)](#) and [Aledort et al \(2004\)](#)
- Data available from Amgen's ongoing romiplostim clinical program

The safety data will be assessed annually and the findings will be reported in appropriate context to the regulatory agency via the PSUR, and will include the following:

- Total number of subjects and total person-year observation time in each cohort for the current reporting period, and cumulative for all reporting periods
- Current incidence rates of study outcomes based upon data in the current reporting period, and upon cumulative data for all reporting period
- Average platelet counts in predefined romiplostim treatment periods
- Detailed descriptions of each case of BM fibrosis associated with clinical signs in the current reporting period
- Detailed description of hematological malignancy cases (eg, AML and MDS)

[figure not shown]
A final report to the regulatory agency will be completed within 9 months following the availability of all national data. The final report will be comprehensive for all primary and secondary objectives, and for related outcomes listed in [Section 12](#).

Expected Contribution of Study Results to Current Knowledge

- Determine acute and long-term safety in real life clinical practice
- Describe the impact of romiplostim therapy on platelet count during treatment, and changes after treatment cessation
- Describe the impact of romiplostim therapy on BM fibrosis
- Describe romiplostim off-label utilization pattern

Sponsor/Licensee: Amgen Inc.

Study Design and Patient Registry Schema

Study Glossary and Definition

Abbreviation/Acronym	Definition
AGS	Amgen Global Safety
AML	Acute myelogenous leukemia
BM	Bone marrow
Chronic ITP cITP	Patients who have been diagnosed with ITP for more than 6 months, and who continually receive ITP treatments (eg, ITP related medication) and/or have had a splenectomy procedure
CIMF	Chronic idiopathic myelofibrosis (primary myelofibrosis)
Confounders	Extraneous factors that account for a difference in disease frequency between the exposure groups; associated factors serving as surrogates for these factors are also commonly called confounders
ICD-10	International Classification of Diseases – 10 th Revision
Index date	Date the patient received initial romiplostim therapy in the study period, and the start date of follow-up for each study subject in the Unexposed Cohort
ITP	Idiopathic (immune) thrombocytopenic purpura
Length of disease	Time period from initial diagnosis of the disease to date of study event
MDS	Myelodysplastic syndromes
NCPRR	Nordic Country Patient Registry for Romiplostim
NHRS	National Health Registry System

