3.4 Selection of Participants (or Subject Eligibility)

3.4.1 Inclusion Criteria

Subjects in the NCPRR will be those whose health information is recorded by the NHRS of Denmark, Norway, or Sweden.

The eligible adult cITP romiplostim-exposed patients for the NCPRR must meet all of the following criteria:

- Patients must be 18 years or older at the time of chronic ITP diagnosis,
- Patients will have romiplostim therapy between 01 January 2009 and 31 December 2018, and
- Patients will have at least 6 months of medical information prior to initial date of receiving romiplostim treatment (Index Date), data from which will establish a baseline of study subjects.

The eligible adult cITP romiplostim-unexposed patients for the NCPRR must meet all following criteria:

- Patients must be 18 years or older at the time of chronic ITP diagnosis,
- Patients will not have received romiplostim therapy prior to or during the study period between 01 January 2009 and 31 December 2019, and
- Patients will have at least 6 months of medical information in the study period. The data from this period will establish baseline of subjects in the comparison group.

Eligible romiplostim-unexposed cITP patients will be the source of comparison cohorts for romiplostim-exposed cITP patients. Because potential confounding factors (eg, severity of ITP condition) may cause some biases for the study, however, robust propensity scoring and adjusted analyses will be essential ([Section 12](#)). In addition, appropriate contextualization from other recognized data sources will be used in comparisons to address selection biases.

In addition, according to initial dates of receiving romiplostim therapy among patients in the Exposed Cohort, the follow-up time period will be separated into 2 periods: (1) follow-up time period prior to romiplostim exposure, and (2) follow-up time period following romiplostim exposure. Patient experiences in the follow-up time period prior to the initial date of receiving romiplostim therapy will be considered as another “within-patient” comparison with the patient experiences during the follow-up time period after the initial date of receiving romiplostim therapy.

Eligible romiplostim Off-Label-Exposed patients will be any patient who received romiplostim therapy without an adult chronic ITP diagnosis.

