4.1 Sub-Patient Group Identification

The adult chronic ITP study population is identified using diagnostic codes (ICD-10: D69.3-D69.4) for at least 6 months after the first primary ITP diagnosis, and as having received at least 1 ITP medication, and/or had a splenectomy procedure during this 6-month time period. Electronic medical records will be reviewed to confirm the diagnosis. Confirmation of the diagnosis of ITP will be carried out by clinical presentations and/or related treatment. Based upon the status of romiplostim therapy, these patients will be segregated into the Exposed Cohort and the Unexposed Cohort. The index date for patients in romiplostim Exposed Cohort is defined as the first date of receiving romiplostim therapy.

The Index Date in the exposed cohort will be the date of first exposure to romiplostim. A patient who has not been exposed to romiplostim will have an Index Date imputed based upon the date of diagnosis using 2 methods: 1) if the date of diagnosis is prior to 01 April 2009, the Index Date will be imputed as 01 April 2009 (the first date of romiplostim availability), and 2) if the date of diagnosis is 01 April 2009 or later, the date of diagnosis will be imputed as the Index Date.

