7. REGISTRY FOLLOW-UP PERIOD, EXPOSURE TIME, AND TIME AT RISK FROM EXPOSURE

7.1 Registry Follow-up Period

The follow-up period will be separated into 4 periods:

- Six months prior to receiving romiplostim therapy: This period is considered a cohort qualification and baseline establishment period. Using this period, the eligibility of subjects will be challenged and confirmed, disease conditions will be assessed, and propensity scores will be assigned for each patient. Based on the information, study cohorts will be established.

- Under treatment period: The period is defined as being from Index Date to 10 days after the last dose of romiplostim medication. During this period, all study outcomes will be assessed except for outcomes related to latency effects and post treatment effects.
- Period immediately after romiplostim treatment cessation: This period is defined as between 10 to 100 days after the last dosing. The period will be used to assess risk of worsened thrombocytopenia after treatment cessation (eg, platelet counts, bleeding, as well as rescue medication usage). As needed, this study will separate this time period into 2 sub-time periods: (3a) time period from 10 to 30 days after the last dose; and (3b) time period from 30 days to 100 days after the last dose.
- Post treatment period: This is defined as the period from 100 days after the last dosing to the end of the study. This period, as well as the aforementioned 3 periods, will be used to study long term effects of romiplostim (eg, malignancies).

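### Chronic-ITP status is not judged at the first romiplostim dose, so a start before month 6 of ITP is filed as exposed or off-label according to what happens afterwards

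*Protocol*

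**What the plan says.** The Synopsis (Summary of Subject Eligibility Criteria) describes chronic ITP patients as "defined as those who have been diagnosed with ITP for more than 6 months, and who continually receive ITP treatments", or who have had a splenectomy. No date is attached at which this must be true.

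Section 4.1 makes the definition operational by looking forward. It requires ITP codes "for at least 6 months after the first primary ITP diagnosis, and as having received at least 1 ITP medication", or splenectomy, within that 6-month window. The cohort split comes afterwards: "Based upon the status of romiplostim therapy, these patients will be segregated into the Exposed Cohort and the Unexposed Cohort". The same section then sets the time origin: "The Index Date in the exposed cohort will be the date of first exposure to romiplostim". Section 7.3 counts time at risk from initial exposure.

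Section 3.4.1 sets three conditions for exposed patients: age 18 or over at chronic ITP diagnosis, romiplostim between 2009 and 2018, and 6 months of medical information before the first dose. The last condition concerns records, not duration of ITP. For the off-label description, the Synopsis (Study Design) says that "the study will also include patients without an adult chronic ITP diagnosis, but who are exposed to romiplostim", and Section 3.4.1 defines that group without a date: "Eligible romiplostim Off-Label-Exposed patients will be any patient who received romiplostim therapy without an adult chronic ITP diagnosis".

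Section 7.1 treats the 6 months before romiplostim as a qualification and baseline period and says "Using this period, the eligibility of subjects will be challenged and confirmed". It states no rule on disease duration.

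**The concern.** Cohort membership should be decided by what is known at time zero. Here time zero for an exposed patient is the first dose, but the chronic-ITP condition may be met only later, on treatment. Nothing in Section 4.1 stops romiplostim itself from being the ITP medication that helps to satisfy the definition.

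Two things are at stake. First, the Exposed Cohort acquires a stretch of time in which death could not have occurred, and an early event in a patient who dies before month 6 leaves the exposed rates. Section 2.3 lists thrombotic complications as a potential risk, so early fatal events are among those the registry should capture. Second, the off-label description is a stated objective, and the number of adults with early ITP who appear in it depends on how their disease ran after treatment began.

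**Working it through.** **Tracing the definitions.** Take two adults with 6 months of prior records, each given a first dose at month 3 after ITP diagnosis.

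- Patient A is still coded and treated at month 6. Section 4.1 makes A a chronic ITP patient, and the split by romiplostim status puts A in the Exposed Cohort with Index Date at month 3. Under Section 7.3, months 3 to 6 are exposed time at risk. A could only be classified this way by surviving them.
- Patient B dies or remits at month 4. The 6-month condition in 4.1 is not met, so no adult chronic ITP diagnosis exists and 3.4.1 makes B off-label.

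Status on the first-dose date was identical; only the later course differs. Section 5.1 compounds this by selecting charts for abstraction on ITP of 6 months or more, so B may also receive less chart review.

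**Reproducing the plan's size (Section 3.5).**

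- Prevalent: 570 × 13 = 7,410; × 0.20 = 1,482; × 0.95 = 1,408; × 0.25 = 352.
- Incident: 5,700 × 0.20 = 1,140; × 0.95 = 1,083; × 0.25 = 271.
- Exposed Cohort: 352 + 271 = 623, as stated. The 4,234 patient-years are taken as given, because no follow-up schedule is shown from which to rebuild them.

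**Person-time involved.** The documents give no share of starts before month 6, so this is an assumption with a range: guaranteed-survival time = 271 × (share starting early) × (years left to month 6).

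| Share early | Years left | Patients | Patient-years | % of 4,234 |
|---|---|---|---|---|
| 10% | 0.25 | 27 | 6.8 | 0.16 |
| 30% | 0.25 | 81 | 20.3 | 0.48 |
| 100% (ceiling) | 0.5 | 271 | 135.5 | 3.2 |

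The denominator effect is therefore small even at the extreme.

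**Numerator.** Each event that leaves the Exposed Cohort lowers its rate by about 1,000 / 4,234 = 0.24 per 1,000 patient-years, ignoring the small change in the denominator. How many would leave cannot be estimated from the documents. The direction is fixed: events in patients who die before month 6 can only be lost from the exposed rates, never added.

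**The case against.** The strongest reply is that Section 7.1 already fixes eligibility before the first dose, so later course cannot matter. That would hold if 7.1 required ITP to have lasted 6 months by then. It does not, and the criteria it would confirm, in 3.4.1, contain no such rule. For the same reason a reader might infer that 7.1 bars early starters from the Exposed Cohort and so contradicts the Synopsis, which admits any adult chronic ITP patient with one dose. The text does not support that either: 7.1 bars no one by itself and simply needs aligning.

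A reader might also apply the 80% durable remission in Section 3.5 and conclude that about 20 of every 100 early starters become exposed and 80 off-label. That figure is a planning value for all adult ITP. It carries no 6-month time point, and the note to Figure 1 includes acute cases, successful splenectomies and successful treatment with other compounds. It does not describe patients started on romiplostim early, so no split or percentage undercount can be drawn from it.

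It is fair to say that the off-label objective is framed by patient rather than by start, and that no count of early-ITP starts is promised. Section 12.2 describes utilization among chronic ITP users, and Section 12.7 includes a stratum under 1 year. So persisting early starters are not invisible, but the off-label group is still selected on later course.

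Nor are outcomes for off-label patients simply absent. Section 3.1 has data extracted for all recipients to evaluate the Section 6.2 endpoints. What stands is that Section 12.11 lists person-time, utilization, disease and demographics, and names no event rates.

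Finally, Section 4.1 imputes the unexposed Index Date from the date of diagnosis. If that means first ITP diagnosis, incident unexposed patients may carry guaranteed time too. That bears on the exploratory comparisons, not on the exposed-cohort rate in the primary objective.

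Date rules are often left to the analysis plan. Here, however, the protocol states the rules, and together they condition on the future.

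**Conclusion.** The concern holds as a flaw in classification. On the protocol's own definitions, a first dose before month 6 of ITP is filed by post-treatment course, and those filed as exposed have guaranteed survival to month 6. The filing follows from reading 3.4.1, 4.1 and 7.3 together; the protocol does not describe the case in words.

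The size is unknown. With 10-30% of the 271 incident users starting early and 3 months to run, both assumptions, about 7-20 patient-years (0.2-0.5%) are involved. The exposed denominator is hardly touched. The consequence is selective: early fatal events can leave the exposed rates, and the off-label count depends on remission or death. In a descriptive safety registry this should be corrected, but it does not undermine the study.

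**What to change.** In Sections 3.4.1, 4.1, 7.3 and 12.11:

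- classify every romiplostim start by ITP status on the first-dose date;
- begin Exposed Cohort time at risk at the later of the first dose and the date on which the chronic ITP definition is met;
- report all starts before that date as a separate early-ITP group, whatever the later course, with person-time and Section 6.2 events, so that early on-treatment events are not lost.

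Align Section 7.1 by saying what disease status its qualification period confirms.

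The cost is protocol wording and one derived date per patient, built from the diagnosis and treatment dates already held. The Index Date can stay at first dose, so the baseline window and treatment periods need not move. There is a real downside: a few patient-years, and any early on-treatment events, pass from the Exposed Cohort rates to the separately reported group, and late entrants are already on drug when they enter. The early-ITP group should therefore be shown beside the Exposed Cohort in the annual and final reports.
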